1.10 Regulatory B-cells in food allergy: B-lymphocytes are cells specialized for producing antibodies, and play a crucial role in the pathogenesis of milk allergy by producing IgE, the primary trigger for CMA associated with anaphylaxis. In addition to this already important role, B-cells likely play other crucial roles in the ability tolerate milk proteins. B-cells can produce cytokines such as IL-13, which may contribute to allergic inflammation in lungs and sinuses (39) and increase IgE production. Additionally, as with T-cells, B-cells can play an active role as regulatory cells (B-reg) in various infectious and inflammatory processes. B-reg produce regulatory cytokines, such as IL-10 and TGF β , similarly to T-reg, which can influence the production of IgG4 and IgA. An imbalance in B-reg has been shown to be important to the pathogenesis of Multiple Sclerosis (40). Recently, Noh et al showed that children with eczema and sensitivity to milk had fewer milk specific B-reg than children who could drink milk without worsening of their skin symptoms (32, 41). No studies have examined the correlation between B-reg and IgE-mediated milk allergy and anaphylaxis. Since B-cells can make both pathogenic IgE (which requires IL-13) and regulatory antibodies IgG4 and IgA, (which require IL-10) understanding the contribution of B-reg to milk desensitization is an important facet of clarifying the immunological network that is in play in this disease. Thus we will examine the total numbers of B-reg (designated by the surface markers CD19 and CD5 as well as the cytokines IL-10 and TGF β) and determine changes in these cells in children undergoing oral immunotherapy to milk compared to an observation group of untreated children with milk allergy.

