2.0 Hypothesis: Children who are allergic to milk can be treated via a supervised program of oral immunotherapy (OIT). Successful treatment will be indicated by the ability to ingest dairy products daily with no adverse symptoms. This will be accompanied by a decrease in specific IgE to milk, an increase in IgA and IgG4 blocking antibodies and by increases in milk-specific Regulatory T-cells (Treg) and Regulatory B-cells (Breg).

2.1 Specific Objectives: 1) To determine the efficacy of Oral immunotherapy (OIT) treatment for children with IgE mediated cow's milk allergy (CMA)

2) To determine the safety of OIT for treatment of children with IgE-mediated CMA

3) To determine if successful OIT for children with CMA is associated with increases in blocking antibodies, including milk specific IgA and IgG4

4) To determine if successful OIT for children with CMA is associated with increases in Treg and/or Breg.

2.2 Rationale: CMA is a very common problem in children with important nutritional impact. Moreover, milk is among the most common foods associated with severe allergic reactions and anaphylaxis, and is extremely difficult to avoid. Treatment of CMA is currently based on strict avoidance, which is difficult to adhere to due to the ubiquitous nature of dietary dairy products. Treatment with oral immunotherapy (OIT) has been performed in the USA and Europe, but there are few rigorous, blinded clinical trials, with adequate controls and outcomes. However, there is no current research into OIT for CMA in Canada, depriving our population of a potential cure for this very common problem. A well defined clinical trial with adequate controls and immunological outcomes is essential for understanding the ideal patients and the safest and most efficacious methodologies, and for dissemination of successful milk specific OIT protocols to practitioners for more general use.

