Through a process of stratified randomization (according to sex), participants will be randomly assigned to one of 2 study groups. The first group will receive active desensitization, and the second group will not receive any treatment but will be followed up regularly (Appendix A Table 2). Desensitization will be offered to the observation groups following the trial, should the outcome be successful in the treatment group.

3.2 Oral challenge test to milk. Prior to initiating desensitization and following treatment, the subjects will undergo a placebo controlled oral challenge to milk. These challenges will determine the level at which the children react and will be the baseline to follow their improvement in oral tolerance following therapy.

Oral challenges will be single blinded and will be performed with fresh cow's milk, with increasing doses taken orally every 10 to 15 minutes up to a total of 150ml of milk (doses of 0.1, 0.3, 1.0, 3.0, 10.0, 30.0, 45ml, 60 mL) ^{(49,82) (83)}. Patients will receive 2 challenges per day, 1 placebo and 1 with the active substance (milk). Nurses in the Medical Day Unit/Center for Investigative Medicine will prepare the food and randomize the placebo challenges. Unless contraindicated, the placebo will be soy or rice-based milk. If the challenge is negative after 150 ml of milk, results will be confirmed by means of open challenge, using 250ml of yogurt or ice cream 1 hour after completion of the blinded portion(29) according to the recommendations of the European Academy of Allergology and Clinical Immunology (5). After completing the challenge, patients will be kept under observation for at least 2 hours. Only objective symptoms will be considered to be indicative of a positive allergic reaction (29). Food challenges will be scored as positive if a single symptom or any of the following objective clinical reactions will be observed: urticaria, angioedema, wheezing, rhinitis, vomiting, diarrhea, protracted abdominal pain, exacerbation of atopic dermatitis, or shock. A single episode of vomiting will not be considered as a positive reaction, while severe and repetitive vomiting will. If the challenge is **negative**, ie, the subject is asymptomatic, he/she will be excluded from the study. Based on our experience, approximately 80% of those subjects ages 6 or greater, with positive history and positive skin tests, approached will fail the oral challenge and thus be eligible.

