3.3.3 Maintenance phase

Patients who reach the maintenance dose of 200 ml will be instructed to continue and consume 200 ml of milk daily for 1 month. They will then undergo an oral challenge (see above), with the maximum dose of 300ml.

If this 300 ml dose is tolerated, they will be permitted to consume dairy products without restrictions and attend regular follow up visits for 12 months. It will be recommended to consume dairy at least twice weekly, if not more, to maintain the desensitization.

Subjects who tolerate less than the 200 ml upper dose will be instructed to continue their maximum tolerated dose for the 12 month follow-up period, at which time another blinded milk challenge will be performed to determine if their tolerance increased.

3.3.4 Long Term Follow-up: to assess the persistence of milk desensitization from clinical, cellular and molecular perspectives, participants will be asked to return to the research center once a year for five years following the end of the Maintenance Phase. At these visits, participants will be asked about their dairy consumption, any reactions they may have experienced in the interval between the last visit and changes in their quality of life (as assessed by questionnaire). Participants will also have the following analyses done: SPT, salivary IgA, serum milk-specific IgE, IgA and IgG4 concentrations, Glycosylation state, Vitamin D levels, and B and T cell regulatory cell phenotyping. Participants will be reminded of the importance of continuing the consumption of dairy products in the maintenance of desensitization. Participants who have completed the study will be asked to reconsent to the extension. Given that these participants may not have scheduled visits to the hospital, to lessen their inconvenience, a delegated member of the study team might make a home visit in order to obtain informed consent

3.3.4 Control Subjects: Subjects randomized to no treatment will be followed every 3-6 months as is standard in our clinic for milk allergy. They will have skin testing and blood testing as on routine follow-ups, but they will be required to fill out symptoms diaries. At the end of the study period, oral desensitization will be offered to the control patients who had not spontaneously achieved tolerance.

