3.3.4 Documentation: Subjects and families will be asked to complete daily home diaries to document that daily doses were taken, as well as to report accidental ingestions, problems with dose administration, or related symptoms. Follow-up visits in addition to or in conjunction with the weekly visits for dose escalation will be at 3, 6, 9, 12 months from completion of OIT. Each visit will include a medical history and physical examination, SPT, serum milk-specific IgE, IgA and IgG4 concentrations, Vitamin D levels, and B and T cell regulatory cell phenotyping will be measured at enrollment and at follow-up visits. (see Appendix C). Biweekly or monthly Telephone follow-up of these patients will be done prior to and following reaching the maximum tolerated dose. The telephone follow-up will review symptoms

and protocols for how to treat potential reactions.

3.3.5 Adverse reactions to OIT: All patients and their caregivers (if applicable) will be provided self-administered epinephrine, along with instructions and indications for administration and education about the nature of possible reactions to the desensitization therapy. Home diary forms will be provided to record the dose, date and time taken, symptoms occurring after the dose or any other time, and medications taken each day (Appendix D).

Safety measures: The patients' caregivers will be instructed **verbally and in writing** about the recommendations to be followed after desensitization and how to **treat** possible allergic reactions. They will also be given telephone and pager numbers of investigators and nurses for direct consultation 24/7. Parents will be instructed to contact the research team should any symptoms suggestive of an allergic reaction be present (appendix E, bottom of page).:

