Withdrawal from therapy: Subjects will be carefully monitored during the in hospital rush therapy phase, as well as during the home OIT phase. Instructions for treatment of reactions will be provided as above. Patients who are enrolled will be informed that in previously published studies, minor allergic reactions are common in these protocols (mild itching, abdominal discomfort) but resolve with increased time on therapy. Subjects will be withdrawn if they cannot tolerate the low dose, rush desensitization phase, if they have more than 2 or more moderate or severe reactions during the home (maintenance) OIT phase, if they experience a rare or unforeseen complication such as severe flares of eczema or chronic gastrointestinal symptoms (e.g. development of eosinophilic esophagitis) and if the parents or subjects wish to voluntarily terminate therapy.

3.3.6 : Variables measured. The following variables will be measured in each patient:

A. The primary outcome measure will be the presence of desensitization defined by the ability to tolerate 200 ml of milk 1 year after the start of the trial. This is a qualitative variable with three categories: total desensitization (200 mL of cow's milk); partial desensitization (20–200 mL); and failed desensitization (<20 mL milk). Only patients presenting total desensitization were regarded as being successfully desensitized.

B. Secondary outcome measures will be:

1. Number and severity of adverse reactions occurring after oral exposure to milk during the desensitization and follow-up phases.
2. Minimum dose of milk that triggered symptoms during the desensitization protocols or challenge tests.
3. Days until desensitization was achieved.
4. Indices of desensitization :
 - a. Change in skin prick test weal size, comparing tape transferred, cpoputor measured diameters and areas of the skin tests to milk extract.
 - b. Levels of sIgE, sIgA and sIgG4 before desensitization, during follow-up and at the end of the study.
 - c. T and B reg before desensitization, during follow-up and at the end of the study.

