4.0. Statistical Considerations

A: Sample Size calculation: Given that previous studies have attributed at least 50% improvement in the ability to tolerate milk(24) with an α of 0.05 and a power (1- β) of 0.80, a sample of 42 cases and 42 controls will be recruited.

B: Statistical Analysis: Statistical analyses will be performed using paired t-tests. A p value of <0.05 will be considered significant. Descriptive statistics of the variables including means, standard deviations and frequencies were computed for all study variables. The concentrations of milk –specific IgE, IgG and IgA, the size of the skin tests , T reg and Breg expression at the different study time-points will be compared with their baseline values using the one-sample paired t-test and to the control using a 2 sample t-test .

Multiple regression models will be used to assess factors associated with response to desensitization, including baseline demographic characteristics; gender; age; baseline SPT and specific IgE, Treg and Breg numbers, and vitamin D level.

5. Ethical Considerations

In the consent form given at study enrolment, participants will be advised that they will be randomly assigned to either oral immunotherapy or observation for a one year period. Participants will also be advised that their data will be shared only among the OIT study team. Participants in the observation control group who will not receive OIT treatment, will be told that they may to undergo such therapy after a year of observation and a positive oral food challenge.

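### The OIT-versus-control test of the immune and skin-test markers leaves out the baseline value already collected, so precision is probably lost on secondary outcomes.

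*Combined protocol and SAP*

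**What the plan says.** Section 4.0.B names paired t-tests as the general method. For the markers, it says that values at the various time-points will be "compared with their baseline values using the one-sample paired t-test and to the control using a 2 sample t-test". Read literally, the between-arm test uses visit values.

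Other sections speak of change:
- The Experimental Approach summary refers to changes in IgE, IgG4, IgA and regulatory T and B cells.
- Section 1.10 plans, for Breg, to "determine changes in these cells in children undergoing oral immunotherapy to milk compared to an observation group of untreated children with milk allergy".
- Sections 3.3.8 and 3.3.9 follow changes in Treg and Breg over time.
- Section 3.3.6 lists "Change in skin prick test weal size" for the skin test, but levels for the antibodies.

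Baseline values exist: section 3.3.4 (Documentation) says that "B and T cell regulatory cell phenotyping will be measured at enrollment and at follow-up visits", and Appendix C puts the first immune panel at Visit 1. Section 3.1 stratifies randomisation by sex. The only model with covariates in section 4.0.B concerns predictors of response to desensitization, not the difference between arms.

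On timing, section 3.3.4 (Control Subjects) states: "Subjects randomized to no treatment will be followed every 3-6 months as is standard in our clinic for milk allergy". Section 5 lets controls start OIT after a year of observation and a positive challenge. Section 3.1 cites a control schedule in Appendix A Table 2, which is not in the available text.

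**The concern.** The markers are secondary outcomes and bear on two of the four objectives. A baseline value usually predicts the follow-up value of the same marker in the same child. A between-arm test that ignores it leaves that variation in the error term, although the data are already being collected.

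Two further points follow from the same sentence. First, the plan does not say which of its two tests supports a statement about OIT. The paired test ignores the randomised controls, and section 1.5 notes that milk allergy can resolve with age, so a within-arm change should not by itself be credited to treatment. Second, with no fixed scale and no key visit, the reported comparison could be chosen after the data are seen.

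**Working it through.** **Inputs from the documents.** 42 per arm, alpha 0.05 and power 0.80 (section 4.0.A). Sidedness is not stated; two-sided is assumed.

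**Inputs assumed.** The correlation ρ between baseline and follow-up is not given, so a range is used. SD = 1 at both times and in both arms, normal data, and all 42 per arm analysable unless stated.

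**The plan's own figure.** The 42 per arm cannot be rebuilt, because the control rate, SD and sidedness are missing. A 50-point absolute difference in proportions needs 11 to 15 per arm without continuity correction. A difference of about 0.615 SD gives 42, but that figure is not in the text. The check below takes 42 as given.

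**Residual variance (SD² = 1).**
- Visit values: 1.
- Changes: 2(1 − ρ).
- ANCOVA: (1 − ρ²) × 81/79. The second factor, (N − 3)/(N − 5) with N = 84, is 1.025 and is the average cost of estimating two covariates.

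**Detectable difference.** The normal approximation on visit values is (1.960 + 0.842) × √(2/42) = 0.611 SD. The noncentral t gives 0.619 SD. Noncentral-t results in SD units (df 82, 82 and 80):

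| ρ | Visit values | Changes | ANCOVA |
|---|---|---|---|
| 0.3 | 0.619 | 0.732 | 0.598 |
| 0.5 | 0.619 | 0.619 | 0.543 |
| 0.7 | 0.619 | 0.479 | 0.447 |
| 0.9 | 0.619 | 0.277 | 0.273 |

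Simulating the ANCOVA at its detectable difference for ρ = 0.3, 0.5 and 0.7 gave power of 80% each time.

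**Equivalent sample size of ANCOVA with 42 per arm.**
- Against visit values, 42 / [(1 − ρ²) × 1.025]: 45, 55 and 80 per arm at ρ = 0.3, 0.5 and 0.7.
- Against changes, 42 × 2(1 − ρ) / [(1 − ρ²) × 1.025]: 63, 55 and 48 per arm.

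**Power for a true difference of 0.4 SD.** Visit values 44%; changes 33, 44 and 65%; ANCOVA 47, 54 and 71% at the same three correlations.

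**Where ANCOVA stops gaining.** Against visit values it needs (1 − ρ²) × 1.025 < 1, so ρ above about 0.16. Against changes it needs (1 + ρ)/2 × 1.025 < 1, so ρ below about 0.95.

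**Loss of patients.** With 38 analysable per arm (an assumed loss of about 10%), visit values give 0.65 SD; changes 0.77, 0.65 and 0.50 SD; ANCOVA 0.63, 0.57 and 0.47 SD.

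**Sex term.** With a 50:50 split and an assumed sex difference of g SD, the variance factor is 1 − g²/4. For g = 0.2, 0.3 and 0.5, power at 0.619 SD rises from 80% to 80.4, 80.9 and 82.5%.

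**Number of between-arm visits.** Control visits every 3 to 6 months for one year give 12/6 = 2 to 12/3 = 4 occasions.

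**Timing.** If completion of OIT means reaching 200 ml, at about week 17 in Appendix B, then Visits 26, 27 and 28 (6, 9 and 12 months later) fall near weeks 17 + 26 = 43, 17 + 39 = 56 and 17 + 52 = 69. None is at week 52, and the last two fall after the control year.

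**The case against.** The best reply is that nothing here is wrong, only less efficient than it could be. A two-sample t-test between randomised arms is valid. In simulation under no effect, the tests on values and changes and the ANCOVA all rejected close to 5% of the time (4.3 to 5.3%). The correlation is unknown. At 0.3 the gain over visit values is small (0.62 to 0.60 SD), and at very high correlation the gain over changes is small too. The sex term adds almost nothing. All of this stands and limits the point to a modest one.

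A second reply is that measurement scale may matter more than adjustment. This also stands. ImmunoCAP IgE is bounded at 0.35 and 100 (section 3.1) and may be skewed. As an illustration, assume log-normal IgE with median 15 and log-SD 1.5, cut at those limits, with a true shift of 0.6 log-SD. A t-test on raw values then has about 63% power, and raw ANCOVA 65, 71 and 82% at ρ = 0.3, 0.5 and 0.7. A plain t-test on logs has about 77%. The scale must therefore be part of the remedy.

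A reader might also infer that Appendix C offers seven post-baseline visits (Visits 22 to 28) from which to pick a result. The documents do not support that for the between-arm test. Those visits follow the OIT schedule, and a comparison needs control samples too, which leaves about two to four occasions.

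**Conclusion.** The point holds as a probable loss of precision on secondary outcomes. Against visit values, the literal reading, baseline adjustment lowers the detectable difference from 0.62 SD to about 0.60, 0.54 or 0.45 SD at correlations of 0.3, 0.5 or 0.7. If changes are meant, it goes from 0.73, 0.62 or 0.48 SD to the same figures. These results rest on assumed correlations, equal SDs, normal data and 42 analysable per arm.

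The missing scale and key visit alone would be missing detail. The core is that a baseline value already collected is not used.

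Two stronger readings are not supported. One is that the marker comparison is biased or that the primary 200 ml outcome is affected; neither follows. The other is that Objectives 3 and 4 fail with this test. Objective 4 reads "To determine if successful OIT for children with CMA is associated with increases in Treg and/or Breg", and Objective 3 is likewise about successful OIT, so neither rests on the whole-arm comparison alone.

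**What to change.** Amend section 4.0.B as follows.

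1. For each marker, make the between-arm comparison an ANCOVA (or a mixed model over visits) of the follow-up value on arm, that marker's baseline value and sex.
2. State the scale in advance, for example logs for specific antibodies, with a rule for IgE values at the 0.35 and 100 assay limits.
3. Base any claim of an OIT effect on this comparison, and report within-arm paired changes descriptively.
4. Keep the association with successful OIT as a separate analysis, because a whole-arm comparison does not separate successful from failed OIT.
5. Name one comparison time shared by both arms, near 12 months from randomisation, using each control's sample taken before that control starts OIT. Treat other shared visits as supportive.
6. Reconcile section 3.3.4 (Control Subjects) with Appendices B and C on visit timing, and on whether OIT participants are on or off OIT at that time. Appendix B lists 200 ml for weeks 17 to 52, while Appendix C dates Visits 24 and 25 from cessation and Visits 26 to 28 from completion.

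The cost is SAP wording and two degrees of freedom (80 instead of 82), with no extra patients. An existing blood draw and skin test may need re-timing if Appendix A Table 2 does not already align the arms.

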In addition, there are major gaps in the understanding of the immunological changes that accompany successful OIT. Individuals who outgrow food allergy have decreased size of allergy skin testing, and exhibit decreases in specific IgE antibodies to milk. Perhaps counter-intuitively, serum IgE against milk does not have to be undetectable, nor the skin test completely negative before a patient can tolerate milk (29). No firm cut-offs for skin test or IgE that will predict tolerance exist, although guidelines have been established that help predict who may undergo oral challenges successfully(30). In order for a child who has CMA to safely ingest milk, other changes in the immune system clearly are required to counter-balance the IgE antibodies that cause the disease. We will review several of the proposed immune system changes that are associated with tolerance to CMA.

1.8 Pathogenic and blocking antibodies: Antibodies are produced by B-lymphocytes (B-cells). To produce antibodies, B-cells must interact with T-lymphocytes, and receive specific signals from cell-cell contact and from intracellular communication molecules known as cytokines. For example, to synthesize IgE, B-cells must receive Interleukin (IL) 4 and/or IL-13 from T-cells. Importantly, patients who become tolerant to an allergen naturally or via immunotherapy exhibit an increase in antibodies of the **IgG4 class** (31). IgG4 may be a sign of tolerance, or may actually act as a “blocking antibody” to counteract IgE. Recently, in subjects being desensitized for peanut allergy, peanut specific **IgA** was also found to increase with treatment. IgA and IgG4 are produced when B-cells are exposed to IL-10 and Transforming Growth Factor β (TGF β), and both IgG4 and IgA may act as blocking antibodies, especially in the intestinal tract (32). It is not yet known if milk specific IgA increases with milk OIT. In this proposal we will follow the progression of milk specific IgE, IgA and IgG4 and correlate these with clinical outcomes.

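### Objectives 3 and 4 ask whether immune changes go with successful OIT, but the planned marker tests never use success status, so they cannot separate success from milk exposure

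*Combined protocol and SAP*

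**What the plan says.** Section 2.1 states objective 3 as "To determine if successful OIT for children with CMA is associated with increases in blocking antibodies, including milk specific IgA and IgG4" and objective 4 as "To determine if successful OIT for children with CMA is associated with increases in Treg and/or Breg". Section 3.3.6 A divides the one-year outcome into total, partial and failed desensitization and adds: "Only patients presenting total desensitization were regarded as being successfully desensitized".

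Section 3.3.3 describes OIT children who do not reach the top dose: "Subjects who tolerate less than the 200 ml upper dose will be instructed to continue their maximum tolerated dose". The OIT arm will therefore contain milk-exposed children who are not successes.

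For antibodies, skin tests, Treg and Breg, section 4.0 B says that values at the study time points will be "compared with their baseline values using the one-sample paired t-test and to the control using a 2 sample t-test". It does not split the OIT arm by outcome, and it names no analysis population.

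Two other statements bear on the point:

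- Section 4.0 B also says: "Multiple regression models will be used to assess factors associated with response to desensitization, including baseline demographic characteristics". The immune terms that it lists are "baseline SPT and specific IgE, Treg and Breg numbers, and vitamin D level".
- Section 1.8, in the background, says of milk-specific IgE, IgA and IgG4 that the investigators will "correlate these with clinical outcomes".

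**The concern.** The objectives concern an association between an outcome (success) and a change (a rise in a marker). The planned tests concern a different pair: assignment to OIT, or time since baseline, and the level of the marker. If milk intake itself raises IgG4, IgA or casein-induced Treg and Breg, both planned tests will be significant even when the rise is just as large in children who were not desensitized.

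The stake is interpretation. A report that markers rose on OIT would be correct, but it would probably be read as confirming objectives 3 and 4, which it would not have tested. Section 1.6 and the text just before it set the wider aim of learning which immune changes predict successful treatment, and the planned tests do not address that either.

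**Working it through.** **1. The plan's own figure.** Section 4.0 A gives 42 per arm, from alpha 0.05, power 0.80 and at least 50% improvement in milk tolerance. This cannot be reproduced, because no control rate or SD is stated. An absolute gain of 50 percentage points needs 11 to 15 per arm without continuity correction. A total of 42 per arm arises only with added assumptions, such as 50% versus 21%. The figure concerns milk tolerance and not the markers, so the point does not depend on it. It supplies only the size of the OIT arm.

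**2. What each statement tests.**

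| Statement | Contrast | Uses success? | Markers |
|---|---|---|---|
| 4.0 B, paired t-test | follow-up v baseline | no | all |
| 4.0 B, two-sample t-test | OIT v control | no | all |
| 4.0 B, regression | response on listed factors | yes | on its plain reading, baseline SPT, IgE, Treg, Breg; IgA and IgG4 not named |
| 1.8, background | unspecified correlation | presumably | antibodies only; no test, time point or population |
| 1.10, background | OIT v untreated | no | Breg |

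No row compares the change in IgA, IgG4, Treg or Breg between successes and non-successes.

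**3. Can the planned tests tell the two explanations apart?** Simulation of 20,000 trials. All values are assumed: 25 successes and 17 non-successes in the OIT arm (about 60% success), 42 controls, changes in SD units, and a mean shift over the OIT arm of 0.8 SD. In scenario (b) the shift in successes is 0.8 × 42/25 = 1.34 SD, and zero in the others.

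| Scenario | Paired v baseline | OIT v control | Success v non-success |
|---|---|---|---|
| (a) exposure only, equal rise in both groups | 99.9% | 95.1% | 4.9% |
| (b) rise in successes only | 99.7% | 92.7% | 98.6% |

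The entries are the share of trials with two-sided p < 0.05. The planned tests behave almost identically under (a) and (b). Only the within-arm contrast separates them.

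**4. Precision of the within-arm contrast.** For a two-sided t-test at 0.05 with 40 degrees of freedom, 80% power needs a noncentrality of about 2.87. The detectable difference is d = 2.87 × √(1/n₁ + 1/n₂), unadjusted and with no loss. The success rates are assumed.

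| Success rate | n₁ v n₂ | √(1/n₁ + 1/n₂) | d (SD) |
|---|---|---|---|
| 50% | 21 v 21 | 0.309 | 0.89 |
| 60% | 25 v 17 | 0.314 | 0.90 |
| 70% | 29 v 13 | 0.334 | 0.96 |
| 80% | 34 v 8 | 0.393 | 1.13 |
| 90% | 38 v 4 | 0.526 | 1.51 |

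With an assumed 20% loss (42 × 0.8 ≈ 34 children), d is 1.01 SD at 60% success and 1.23 SD at 80%. For comparison, 42 v 42 detects 0.62 SD.

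**5. Why cumulative dose should not be in the main model.** From Appendix B, with the 2.5 ml dose taken for 14 days (35 ml) and each later dose for 7 days:

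- The doses for weeks 2 to 17 add to 870 ml, so full escalation gives 870 × 7 + 35 = 6,125 ml.
- A child held at 20 ml from week 8 takes (55 + 10 × 20) × 7 + 35 = 1,820 ml.

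Dose and success are therefore closely tied. If they correlate at 0.7 to 0.9 (assumed), adjustment inflates the detectable difference by 1/√(1 − r²), which is 1.40 to 2.29. It then runs from 0.89 × 1.40 = 1.25 SD to 1.13 × 2.29 = 2.59 SD.

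**The case against.** **The objectives may be meant at group level.** The Experimental Approach and section 3.1 use the word successful for the treatment as a whole, and sections 1.9 and 1.10 plan treated-versus-untreated comparisons. On that reading section 4.0 B tests what was intended. But section 3.3.6 A defines success patient by patient, and the plan nowhere says that objectives 3 and 4 use another meaning.

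**The regression may cover it.** Its covariate list is open-ended, and it is unclear whether the word baseline extends to Treg and Breg numbers. If on-treatment values were meant, the regression would touch objective 4. It would still not name IgA or IgG4, so objective 3 would stay open. The ambiguity is a reason to clarify the text.

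**The tests might be restricted to successes.** Section 4.0 B does not say so. Even then, comparing successes with their own baseline or with untreated controls leaves exposure confounded.

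**Not every OIT child has long exposure.** This stands. A reader might infer that all non-successes take milk for months. The withdrawal rules in section 3.3.5 remove children who cannot tolerate the rush phase or who have repeated moderate or severe home reactions. Some failures will have short exposure and may lack a follow-up sample.

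**The replacement contrast is weak.** This also stands. It is non-randomised and has low power if most children succeed. A marker taken at Visit 22 or 23 gives little real temporal precedence, because by then it is already known whether the child has reached 200 ml. The one-year grouping also needs care: section 3.3.3 specifies the 12-month challenge for those below 200 ml, and Appendix C lists challenges only at Visits 2 and 24.

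**Conclusion.** The concern holds. As written, section 4.0 B contains no test that answers objectives 3 and 4 on the protocol's own definition of success, and neither the regression nor the background statement fills the gap. The size of the problem is shown by the planned comparison with control: it is significant in 95.1% of simulated trials when success plays no part and in 92.7% when success is everything. Those percentages rest on the assumed 0.8 SD shift and 25/17 split. The qualitative result does not, because neither planned test uses success status.

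Two stronger readings are not supported. A reader might infer that the planned tests are invalid. They are not: OIT versus control is a randomised test of whether OIT changes the marker, and only the further claim about success is unsupported. A reader might also infer that efficacy or safety conclusions are affected. Objectives 1 and 2 do not depend on these tests.

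This should be changed but is not critical, since it concerns mechanistic objectives and not the primary outcome.

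**What to change.** In section 4.0 B:

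- Add a pre-specified exploratory comparison within the OIT arm. Compare change from baseline in IgG4, IgA, Treg and Breg between children with total desensitization and all other OIT children who have a follow-up sample, adjusted for the baseline marker value.
- Show the total, partial and failed categories with confidence intervals, and report how many withdrawn children have no sample.
- Name the visit that supplies the marker and the assessment that supplies the one-year category.
- Keep cumulative milk dose out of the main model. Show it descriptively or as a sensitivity analysis.
- Keep OIT versus control as the test of whether OIT changes the marker. Claim an association with successful OIT only from the within-arm contrast.
- State whether the Treg and Breg terms in the regression are baseline values.

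The cost is a paragraph of text and one further model per marker, on blood samples already scheduled in Appendix C. No dose, visit or sample changes. The downside is that the contrast is non-randomised and imprecise (the detectable differences above, larger with dropout), so the claim for objectives 3 and 4 may become weaker.
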